3. INTRODUCTION

This SAP has been developed after review of the Clinical Study Protocol (final version dated 24 July 2017 and Protocol Amendment (c) (final version dated 06 September 2017).

This SAP describes the planned analysis of the safety, tolerability, pharmacokinetic (PK) and pharmacodynamic (PD) data from this study. A detailed description of the planned TFLs to be presented in the clinical study report (CSR) is provided in the accompanying TFL shell document.

The intent of this document is to provide guidance for the statistical and PK analyses of data. In general, the analyses are based on information from the protocol, unless they have been modified by agreement between Eli Lilly and Company and Covance Early Clinical (EC) Biometrics. A limited amount of information concerning this study (e.g., objectives, study design) is given to help the reader's interpretation. This SAP must be signed off prior to first subject administration for this study. When the SAP and TFL shells are agreed upon and finalized, they will serve as the template for this study's CSR.

This SAP supersedes the statistical considerations identified in the protocol; where considerations are substantially different, they will be so identified. If additional analyses are required to supplement the planned analyses described in this SAP, they may be performed and will be identified in the CSR. Any substantial deviations from this SAP will be agreed upon between Eli Lilly and Company and Covance EC Biometrics and identified in the CSR. Any minor deviations from the TFLs may not be documented in the CSR.

This SAP is written with consideration of the recommendations outlined in the International Conference on Harmonisation (ICH) E9 Guideline entitled Guidance for Industry: Statistical Principles for Clinical Trials¹ and the ICH E3 Guideline entitled Guidance for Industry: Structure and Content of Clinical Study Reports².

4. STUDY OBJECTIVES

4.1 Primary Objective

- To assess the abuse potential of lasmiditan compared to the positive control alprazolam and placebo.

4.2 Secondary Objectives

- Further characterize the abuse potential of lasmiditan with additional Drug Effects and Drug Similarity Visual Analog Scale (VAS) measures
- Safety evaluations
- PK of lasmiditan

4.3 Tertiary/Exploratory Objective

- PK of alprazolam

5. STUDY DESIGN

This study is a Phase 1, randomized, subject- and investigator-blind, placebo- and active-controlled, crossover clinical trial in adult subjects who are recreational poly-drug users. This study includes 4 phases:

Screening Phase: Subjects will sign informed consent before their entry to the study and completion of all screening procedures. Screening visits should be within 28 days of dosing in Qualification Phase. Subjects who fail screening may not be rescreened.

Qualification Phase: Eligible subjects who meet all inclusion criteria and none of the exclusion criteria will enter a subject- and investigator-blind placebo-controlled, 2-period crossover design Qualification Phase. Subjects will be randomized to a test dose of 1 mg alprazolam and placebo in a crossover manner with a washout period of at least 3 days (72 hours) between each dose. “Drug-liking” response will be assessed before and after alprazolam and placebo administration using a 100 mm bipolar Drug Liking VAS. Only subjects who meet alprazolam qualification criteria as detailed below will be eligible to enter the Treatment Phase.

In order to qualify for the Treatment Period of the study, subjects must demonstrate the ability to discriminate an alprazolam test dose from placebo, using the 100 mm bipolar Drug Liking VAS, as defined by:

- Acceptable placebo response ranging from 40 to 60 (inclusive) on the 100 mm bipolar VAS for Drug Liking “at this moment”.
- ≥ 15 mm increase in “liking” alprazolam more than placebo.
- Subject is able to tolerate the 1 mg dose of alprazolam, as judged by the investigator, including the ability to complete all PD assessments within 4 hours postdose.
- General behavior suggests that the subject could successfully complete the study, as judged by the study site personnel.

On a case-by-case basis, a subject who meets all of the above criteria, with the exception of sporadic erroneous responses, may be permitted into the Treatment Phase, provided that the investigator or designee determines that the subject’s response was made in error and that the subject can be successfully retrained regarding proper completion of that assessment.

Treatment Phase: This will be a subject- and investigator-blind, placebo- and active-controlled, 5-period crossover design. Subjects will be randomized to 1 of 10 dosing sequences; each dosing sequence consists of 5 dosing periods that evaluate the abuse potential of 1 of the 5 study treatments: placebo, 2 mg alprazolam, and 100 mg lasmiditan, 200 mg lasmiditan, and 400 mg lasmiditan. The washout period between each dose should be at least 3 days (72 hours).

Eligible subjects will be admitted to the clinical research unit (CRU) on Day -1 before the planned study drug dosing during each of the dosing periods in both the Qualification Phase and Treatment Phase. After verification of subjects’ eligibility, including a urine drug screen at time of CRU admission, blinded study drug will be administered on Day 1 after an overnight fast. Abuse potential will be assessed using Drug Effects VAS Battery. Adverse events (AEs), vital

signs, and electrocardiograms (ECGs) will be monitored, and PK samples will be collected according to the Study Schedule (Section 2 of the protocol).

Follow-up Phase: Subjects will have a follow-up visit approximately 1 week after their last dose of study drug, and will present to the CRU for discharge from the study as deemed appropriate by the investigator. Subjects who discontinued from the study before its completion will be asked to attend an Early Discontinuation visit (according to the Study Schedule [Section 2 of the protocol]) approximately 1 week after the last dose of study drug dosing. Figure 1 illustrates the study design.

Figure 1. Illustration of study design

Screening Phase	Qualification Phase		Treatment Phase					Follow-up Phase
Screening Visit	Period 1	Period 2	Period 1	Period 2	Period 3	Period 4	Period 5	Discharge Visit
up to 28 days	3 days	3 days	3 days	3 days	3 days	3 days	3 days	Approx. 1 week after last dose
			Placebo	Las-low	Alprazolam	Las-med	Las-high	
			Las-low	Las-med	Placebo	Las-high	Alprazolam	
			Las-med	Las-high	Las-low	Alprazolam	Placebo	
			Las-high	Alprazolam	Las-med	Placebo	Las-low	
	Alprazolam	Placebo	Alprazolam	Placebo	Las-high	Las-low	Las-med	
	Placebo	Alprazolam	Las-high	Las-med	Alprazolam	Las-low	Placebo	
			Alprazolam	Las-high	Placebo	Las-med	Las-low	
			Placebo	Alprazolam	Las-low	Las-high	Las-med	
			Las-low	Placebo	Las-med	Alprazolam	Las-high	
			Las-med	Las-low	Las-high	Placebo	Alprazolam	

Abbreviations: High = high (400 mg) dose; Las = lasmiditan; Low = low (100 mg) dose; Med = medium (200 mg) dose.

6. TREATMENTS

The following is a list of the study treatment abbreviations that will be used in the TFLs.

Phase	Study Treatment Name	Treatment order in TFL
Qualification Phase	Placebo	1
	1 mg alprazolam	2
Treatment Phase	Placebo	3
	2 mg alprazolam	4
	100 mg lasmiditan	5
	200 mg lasmiditan	6
	400 mg lasmiditan	7

7. SAMPLE SIZE JUSTIFICATION

The study design and analysis methods are as prescribed in “Assessment of Abuse Potential of Drugs: Guidance for Industry” published by the US Food and Drug Administration (FDA), January 2017 (FDA 2017)³. Three different hypothesis tests are of primary interest:

1. Validation test of the sensitivity and integrity of the study: Does the positive control (C) produce mean responses that show greater abuse potential compared to placebo (P)?

$$H1_0: \mu_C - \mu_P \leq \delta_1 \text{ versus } H1_a: \mu_C - \mu_P > \delta_1 \text{ where } \delta_1 > 0$$

2. Does the test drug (T) produce mean responses that show less abuse potential compared to positive control?

$$H2_0: \mu_C - \mu_T \leq \delta_2 \text{ versus } H2_a: \mu_C - \mu_T > \delta_2 \text{ where } \delta_2 \geq 0$$

3. Does the test drug produce mean responses that show similar abuse potential, compared to placebo?

$$H3_0: \mu_T - \mu_P \geq \delta_3 \text{ versus } H3_a: \mu_T - \mu_P < \delta_3 \text{ where } \delta_3 > 0$$

Approximately 60 subjects will be randomly assigned to 1 of 10 treatment sequences, in order to get approximately 50 completers. Subjects who are randomized but who do not complete all 5 periods during the Treatment Phase may be replaced. Replacement subjects will enter the same treatment sequence as the original subject to complete all 5 periods. Treatment sequence assignment will be determined by the repeated Williams square design, as shown in Figure 1.

This will lead to 90% or more power for testing each of the hypotheses of primary interest listed above, with the following assumptions:

- standard deviation of differences of 16 for the Drug Liking VAS (estimate based on within-subject standard deviation estimate of 11.4 from previous studies [Blanchard et al. 2010]⁴)
- actual mean difference between alprazolam and placebo of 22 or more for the Drug Liking VAS,
- actual mean difference between alprazolam and lasmiditan of 12 or more for the Drug Liking VAS,
- actual mean difference between lasmiditan and placebo of 7 or less for the Drug Liking VAS,
- $\delta_1 = 15$, $\delta_2 = 5$, and $\delta_3 = 14$; and
- one-sided significance level of 0.05.

The margin for comparing alprazolam with placebo (δ_1) is defined as 15 mm, based on the 2017 FDA guidance, stating that there should be a difference of at least 15 points between placebo and positive control response. The margin for comparing alprazolam with lasmiditan (δ_2) is defined as 5 mm, based on the need to show that lasmiditan shows some non-negligible lower abuse potential compared to positive control. The margin for comparing lasmiditan with placebo (δ_3) is defined as 14 mm. Consistent with FDA advice, the margin for comparing lasmiditan with placebo (δ_3) is less than the margin for comparing the positive control (alprazolam) to placebo (δ_1).

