Follow-up Phase: Subjects will have a follow-up visit approximately 1 week after their last dose of study drug, and will present to the CRU for discharge from the study as deemed appropriate by the investigator. Subjects who discontinued from the study before its completion will be asked to attend an Early Discontinuation visit (according to the Study Schedule [Section 2]) approximately 1 week after the last dose of study drug dosing.

Study governance considerations are described in detail in [Appendix 3](#).

[Figure LAHB.1](#) illustrates the study design.

Screening Phase		Qualification Phase		Treatment Phase					Follow-up Phase
Screening Visit	Period 1	Period 2	Period 1	Period 2	Period 3	Period 4	Period 5	Discharge Visit	
up to 28 days	3 days	3 days	3 days	3 days	3 days	3 days	3 days	Approx. 1 week	
			Placebo	Las-low	Alprazolam	Las-med	Las-high		
			Las-low	Las-med	Placebo	Las-high	Alprazolam		
			Las-med	Las-high	Las-low	Alprazolam	Placebo		
			Las-high	Alprazolam	Las-med	Placebo	Las-low		
	Alprazolam	Placebo	Alprazolam	Placebo	Las-high	Las-low	Las-med		
	Placebo	Alprazolam	Las-high	Las-med	Alprazolam	Las-low	Placebo		
			Alprazolam	Las-high	Placebo	Las-med	Las-low		
			Placebo	Alprazolam	Las-low	Las-high	Las-med		
			Las-low	Placebo	Las-med	Alprazolam	Las-high		
			Las-med	Las-low	Las-high	Placebo	Alprazolam		

Abbreviations: High = high (400 mg) dose; Las = lasmiditan; Low = low (100 mg) dose; Med = medium (200 mg) dose.

Figure LAHB.1. Illustration of study design for Protocol H8H-MC-LAHB.

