5.4.3. Overall Study Design

The abuse potential will be assessed using a Drug Effects VAS Battery (Section 9.6.1). Due to the subjective nature of these endpoints, the design is subject- and investigator-blind. Subjects and the investigator will be informed of the treatments to be tested in the study; they will be blind to the treatment assignment at each period, which reduces the expectation bias. The crossover design minimizes the inter-individual variability and improves the sensitivity for detecting any differences between treatments. Previous studies on alprazolam suggest that the drug-like effects reduced to neutral about 24 hours after a 1-mg to 3-mg dose, indicating that a 3-day washout period for the Qualification Phase will be adequate (Levy-Cooperman et al. 2016). Based on the PK properties of lasmiditan, a washout period of at least 3 days is deemed adequate for the Treatment Phase; major metabolites are not considered active.

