7.1. Treatment Administered

This study compares single doses of orally administered lasmiditan at 100, 200, and 400 mg with placebo and alprazolam.

Table LAHB.2 shows the treatment regimens.

Qualification Phase: 1 tablet of alprazolam or placebo will be administered orally with approximately 240 mL of room temperature water in the morning, in a sitting position, after an overnight fast.

Treatment Phase: An appropriate number of lasmiditan, alprazolam, and/or placebo tablets will be administered orally with approximately 240 mL of room temperature water, in the morning of each dosing day, in a sitting position, after an overnight fast. The total number of tablets administered in each of the 5 dosing periods will be the same.

Study drugs (alprazolam, lasmiditan, and/or placebo) will be prepared into individual dispensing cups by an unblinded pharmacist and administered by an unblinded staff member who will not be involved in any study assessment procedures. Subjects will be blindfolded prior to each dosing session for each period during the Qualification and Treatment Phases. The unblinded staff member will hand the dispensing cup to each subject, who will then self-administer all tablets in the dispensing cup without touching any of the tablets by hand. Neither the Investigator nor any nursing staff involved in the subject assessment will be allowed to witness the study drug administration.

For both phases, water will be allowed 1 hour after study drug dosing, and meals will be allowed approximately 2 hours after study drug dosing. Subjects will not be allowed to lie supine for 2 hours after dosing, unless clinically indicated or for study procedures.

Table LAHB.2. Treatments Administered

Treatment Name	Lasmiditan	Placebo	Alprazolam
Dosage Formulation	Tablet	Tablet	Tablet
Unit dose Strength(s)/Dosage Level(s)	100-mg, 200-mg tablets	Placebo to match lasmiditan	1-mg or 2-mg tablet
Route of Administration	Oral	Oral	Oral

The investigator or designee is responsible for:

- explaining the correct use of the investigational product(s) to the site personnel
- verifying that instructions are followed properly

- maintaining accurate records of investigational product dispensing and collection
- returning all unused medications to Lilly or its designee at the end of the study

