Note: In some cases, sites may destroy the material if, during the investigative site selection, the evaluator has verified and documented that the site has appropriate facilities and written procedures to dispose of clinical materials.

7.1.1. *Packaging and Labeling*

Each lasmiditan tablet contains 100 or 200 mg of active ingredient and is provided as bulk supply in bottles. Placebo tablets look identical to 100- or 200-mg lasmiditan, but contain no active ingredient, and will be provided in similar bulk bottles.

Alprazolam will be obtained from commercial source. The details and presentation of alprazolam will be provided prior to document finalization.

The investigational product will be labeled according to the country's regulatory requirements.

7.2. *Method of Treatment Assignment*

Treatment sequences will be determined using a repeated 5×5 Williams square design ([Figure LAHB.1](#)). The study will be conducted at a single study center, so the respective randomization schedule can be securely maintained by the study center pharmacist who is responsible for dispensing the blinded study medication in accordance with the schedule. The sponsor (or designee) will be responsible for generating each of the randomization schedules and distributing them directly to the study center pharmacist.

7.2.1. *Selection and Timing of Doses*

The doses will be administered at approximately the same times on each day. The actual time of all dose administrations will be recorded in the subject's case report form (CRF).

7.3. *Blinding*

Blinding will be maintained throughout the conduct of the study as described in the separate Blinding Plan.

Emergency codes will be available to the investigator. A code, which reveals the treatment assignment for a specific study subject, may be opened during the study only if the subject's well-being requires knowledge of the subject's treatment assignment.

If a subject's study treatment assignment is unblinded, the subject must be discontinued from further drug administration, unless the investigator obtains specific approval from a Lilly clinical pharmacologist or clinical research physician (CRP) for the study participant to continue in the study. During the study, emergency unblinding should occur only by accessing the study subject's emergency code.

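### The protocol shows the blinded site all 10 treatment sequences by name, so two correctly recognised periods fix the other three; the size of the exposure depends on a recognition rate the documents do not give

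*SAP*

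**What the plan says.** SAP section 5 says "Subjects will be randomized to 1 of 10 dosing sequences" and prints them in Figure 1. SAP section 7 makes that figure the operative list: "Treatment sequence assignment will be determined by the repeated Williams square design, as shown in Figure 1".

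The site's exposure comes through the protocol. Protocol section 7.2 says "Treatment sequences will be determined using a repeated 5×5 Williams square design" and points to Figure LAHB.1 in section 5.1. That figure lists the same 10 rows by period and carries its own key: "Abbreviations: High = high (400 mg) dose; Las = lasmiditan; Low = low (100 mg) dose; Med = medium (200 mg) dose". Under Protocol Signatures in Appendix 3, the principal investigator signs after reading the protocol.

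On blinding, Protocol section 5.4.3 says of subjects and the investigator that "they will be blind to the treatment assignment at each period, which reduces the expectation bias". Section 7.1 adds blindfolding, equal tablet counts, a separate unblinded dosing staff member, and this rule: "Neither the Investigator nor any nursing staff involved in the subject assessment will be allowed to witness the study drug administration". Section 7.2 has the study centre pharmacist hold the randomisation schedule, which protects each subject's assignment but not the list of possible sequences. Section 7.3 refers to a separate Blinding Plan, which is not among the documents.

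**The concern.** A 10-sequence Williams design uses only 10 of the 120 possible orders of five treatments. That is normal and sound. The difficulty is that the people who must stay blind hold the list with treatment names on it. Guessing a treatment once its effects appear cannot be prevented in a trial of this kind. Deducing the next treatment before it is given can be made harder, and the printed figure makes it easier.

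Protocol section 5.4.3 ties the blind to the subjective nature of the endpoints. Staff who believe they know the coming treatment could act on it in three ways: in the VAS training on Day -1 of every period (Protocol section 2.2), in judging whether an adverse event is related (section 9.2), and in decisions to discontinue a subject (section 8.2). Discontinuation matters because the primary analysis uses only subjects who complete all five periods (Protocol section 10.2; SAP section 8.1). In addition, a replacement subject takes the original subject's sequence (SAP section 7). A sequence already decoded would carry over if staff know who is being replaced.

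**Working it through.** **Inputs.** The 10 rows of Protocol Figure LAHB.1, identical to SAP Figure 1, coded P = placebo, L = 100 mg, M = 200 mg, H = 400 mg lasmiditan, A = alprazolam. About 60 subjects randomised and 50 completers (SAP section 7).

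**The plan's own figures.**
- Each treatment occurs twice in every period, and each of the 20 ordered successions occurs twice. The design is a correct repeated Williams square.
- All three primary tests sit 7 mm from their margins (22 − 15, 12 − 5, 14 − 7). With a standard deviation of differences of 16 and 50 completers, power = Φ(7/(16/√50) − 1.645) = Φ(3.094 − 1.645) = 92.6%, or 92.0% by noncentral t. The stated 90% or more is reproduced, and nothing below affects it.

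**How much the list reveals.**
- One identified period: each of the 25 period-by-treatment cells occurs in exactly 2 sequences, so 2 candidates remain.
- Two identified periods: there are 10 pairs of periods × 20 ordered pairs of treatments = 200 combinations. Of these, 100 occur in exactly one sequence and 100 in none. Any two correct identifications therefore leave 1 sequence.
- The two sequences sharing an alprazolam period are mirror images under P↔H and L↔M. One placebo-versus-400 mg judgement separates them.
- If all 120 orders were possible, two identified periods would leave 120/20 = 6.

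**Later periods known before dosing**, if alprazolam and the earlier of placebo or 400 mg are both correctly recognised:

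| Sequence | A in period | First P or H in period | Later periods known |
|---|---|---|---|
| P L A M H | 3 | 1 | 2 |
| L M P H A | 5 | 3 | 0 |
| M H L A P | 4 | 2 | 1 |
| H A M P L | 2 | 1 | 3 |
| A P H L M | 1 | 2 | 3 |
| H M A L P | 3 | 1 | 2 |
| A H P M L | 1 | 2 | 3 |
| P A L H M | 2 | 1 | 3 |
| L P M A H | 4 | 2 | 1 |
| M L H P A | 5 | 3 | 0 |

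Mean = (4×3 + 2×2 + 2×1 + 2×0)/10 = 18/10 = 1.8 of 5 periods. At least one later period is exposed in 8 of 10 sequences; in the two with alprazolam in Period 5, none is.

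If the second recognised treatment is fixed in advance (always placebo, or always 400 mg), later periods are exposed in 6 of 10 sequences, with mean (2×3 + 2×2 + 2×1 + 4×0)/10 = 1.2.

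**Scale over the trial** (60 subjects spread evenly, 60 × 5 = 300 periods), by assumed share of subjects in whom both recognitions are correct under the first rule:
- none: 0 periods
- half: 0.5 × 60 × 1.8 = 54 periods
- all: 60 × 1.8 = 108 periods

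**How far letter codes would help.** Relabelling the treatments gives 12 distinct Williams sets, which together contain each of the 120 orders exactly once. With no key disclosed, the first subject is protected as if all 120 orders were possible. However, the key is common to all subjects: recognising alprazolam, placebo and 400 mg in one completed subject cuts the 12 sets to 2, and one fully decoded subject identifies the set.

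**The case against.** A reader might infer that alprazolam will probably be recognised, because it is sedating and subjects qualify by telling it from placebo, and hence that the trial is in effect unblinded. The documents do not support that.
- Qualification tests 1 mg alprazolam against placebo. It says nothing about telling alprazolam from lasmiditan. Protocol section 5.4.2 describes the two drugs' pharmacokinetic and adverse event profiles as similar, and section 5.5.1 reports somnolence, dizziness, euphoria and hallucination at 400 mg lasmiditan.
- The selected discriminators are the subjects, while the list is with the investigator and site. Subjects are told which treatments are tested; nothing says they see the sequences.
- The primary scale is completed by the subject (Protocol section 9.6.1), so staff knowledge can act only indirectly.
- Protocol section 10.3 and SAP section 9.4.2 plan a sensitivity analysis of everyone dosed in the Treatment Phase and a comparison of dropout among treatments. SAP section 9.5.1 tabulates adverse events for all causalities as well as those judged related.
- The Blinding Plan may restrict access or separate staff further.

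All of this stands, and it limits the size of the concern. The planned analyses partly offset selective completion and adverse event attribution; they do not address expectation. None of it changes the fact that the named list is in a document the blinded investigator must read, which the stated safeguards do not cover.

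**Conclusion.** The point holds as an avoidable weakness in blinding. It is not an error in the Williams square, the model or the power. The deduction is exact: two correctly identified periods determine the sequence. The size is conditional. It rests on correct recognition by staff of alprazolam and of the earlier of placebo or 400 mg. The share of subjects in whom that happens is unknown, so the range under that rule starts at 0 and reaches 108 of 300 periods only if it happens in every subject. The documents do not show that the blind has failed or that the primary result is biased. What justifies acting is the low cost of the change, and the Blinding Plan should be checked first for any control on who sees the figure.

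**What to change.** - In Protocol Figure LAHB.1, remove the named sequence rows and state only that a 10-sequence repeated Williams design is used, or show letters A to E with no key. Removal is preferable, since a common key can be inferred once a few subjects are decoded.
- Redraw the letter-to-treatment assignment at random, because the present list is already in the protocol.
- Hold the sequences and key only in the randomisation schedule kept by the unblinded pharmacist and the sponsor's randomisation function.
- In SAP Figure 1, use letters or restrict the document from blinded site staff.

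The cost is one amendment edit and one regenerated schedule before Treatment Phase dosing; if dosing has begun, the change applies only to subjects not yet randomised to that phase. No extra subjects, procedures or analyses are needed, and the Williams balance, model, sample size and power stay as they are. The change makes it harder to deduce a later treatment before dosing but does not make it impossible.
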